6.6. Study Drug Accountability

The Investigator or designee will maintain accurate records of receipt and the condition of all study drugs including dates of receipt. Accurate records will be kept detailing when and how much study drug is dispensed and used by each patient in the study. Any reason for departure from the protocol dispensing regimen must also be recorded.

Drug accountability records and inventory will be available for verification by the Sponsor Monitor or designee. Periodically throughout the study, there will be a reconciliation of all study drug.

Study drug must not be used for any purpose other than the present study. Study drug which has been dispensed to a patient and returned unused must not be re-dispensed to a different patient.

Further instructions about study drug accountability are detailed in the Pharmacy Manual.

6.7. Study Drug Handling and Disposal

Remaining study drug (all used, partially used, and unused vials) will be returned to the Sponsor or its agent or destroyed at the clinical study center according to applicable regulations.

7. PHARMACOKINETIC ASSESSMENTS

7.1. Blood Sample Collection

Blood samples will be collected for the assessment of plasma levels of revusiran at the time points in the Schedule of Assessments (Table 1).

Exploratory analyses may also be conducted on plasma samples to evaluate metabolites of revusiran.

7.2. Sample Analysis

Pharmacokinetic samples will be analyzed by a central laboratory. Instructions for storage and handling of PK samples can be found in the Study Reference Manual.

8. ASSESSMENT OF EFFICACY

The timing of assessments is in the Schedule of Assessments (Table 1).

8.1. Primary Efficacy Assessment

Serum samples will be collected within 1 hour predose for the measurement of total TTR levels. Samples will be analysed using an enzyme-linked immunosorbent assay method at a central laboratory.

8.2. Secondary Efficacy Assessments

8.2.1. Modified Neurological Impairment Score +7

The mNIS+7 assessment tool is a composite measure of neurologic impairment which includes the following measures:

- Clinical exam-based neurologic impairment score (including NIS weakness, reflexes, and sensation. Note: sensation is not included in the mNIS+7 score)
- Electrophysiologic measures of small and large nerve fiber function (+7) including:
 - Nerve conduction studies (NCS) 5 attributes (Σ 5)
 - Quantitative sensory testing (QST) by body surface area including touch pressure and heat pain
- Autonomic function (postural blood pressure)

A summary of the scoring of the components of the mNIS+7 is in Appendix 16.1.

At each time point, 2 independent assessments will be performed. Each clinical study center will make every effort to have these assessments performed by the same study staff. Assessments are to be performed at least 24 hours (approximately) apart from each other but no greater than 7 days apart. In order to limit potential intra-operator bias, the source documents and results from any of the prior assessments will not be available to the examiner when performing the second assessment.

Every effort will be made to use the same devices for NCS and QST for a patient throughout the duration of the study.

8.2.2. Norfolk Quality of Life – Diabetic Neuropathy Questionnaire

Quality of life will be assessed through the Norfolk QOL-DN questionnaire, a standardized 47-item patient-reported outcomes measure that is sensitive to the different features of diabetic neuropathy-small fiber, large fiber, and autonomic nerve function.[37]

8.2.3. Polyneuropathy Disability Score

Changes in ambulation will be evaluated through the PND score; the PND scale is in Appendix 16.2.[38,39]

8.3. Exploratory Assessments

Additional details can be found in the revusiran Study Reference Manual.

8.3.1. Modified Body Mass Index

Using Body weight data, the mBMI will be calculated (body mass index \times albumin). This calculation will take place programmatically; the calculation will not be performed by the clinical study center staff.

8.3.2. Familial Amyloidotic Polyneuropathy Stage

Changes in ambulation will be evaluated through the FAP stage; the FAP stage scale is in Appendix 16.3.[38,39]

8.3.3. Neurological Impairment Score

The NIS includes measurements of weakness, sensation, and reflexes. The NIS weakness and reflex sub-components are the same as the mNIS+7. The sensory component in mNIS+7 uses QST a more quantitative approach to assessing a broader range of somatic sensory function than the sensory sub-score within the NIS. At each time point, 2 independent assessments will be performed in the same manner as described for mNIS+7.

8.3.4. Grip Strength Test

Hand grip strength will be measured by dynamometer. Clinical study center staff will be trained on the use of a dynamometer and testing for the study. When performing the test, patients will stand, holding the dynamometer in their dominant hand, with their arm parallel to the body without squeezing the arm against the body. Tests will be performed in triplicate on the same study visit day and 2 independent assessments will be performed \geq 24 hours, but \leq 7 days apart. Every effort will be made to use the same dynamometer for a patient throughout the duration of the study.

8.3.5. New York Heart Association Classification

New York Heart Association classification will be recorded. The NYHA classification scale is provided in Appendix 16.4.

8.3.6. Karnofsky Performance Status

Performance status will be assessed according to the Karnofsky Performance Status scale; the scale is in Appendix 16.5.

8.3.7. Echocardiogram

An echocardiogram (ECHO) with Doppler will be used for assessment of cardiac structure and function and will be assessed by a central laboratory.

Details for image acquisition and upload for central review can be found in the revusiran Study Reference Manual.

8.3.8. Cardiac Biomarkers

Blood samples will be collected and analyzed for the quantification of troponin T, troponin I, N-terminal prohormone of B-type natriuretic peptide (NT-proBNP; biomarkers of cardiac status), and B-type natriuretic peptide (BNP). Quantification of these biomarkers will be performed at a central laboratory.

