10.2. Statistical Methodology

A full statistical plan will be finalized before database lock.

The primary efficacy analysis will be performed after all patients have finished 6 months of treatment with study drug.

Analyses will be performed using SAS[®] for Windows (version 9.2 or higher). Descriptive statistics (mean, standard deviation, median, minimum, and maximum) will be presented for continuous variables, and frequencies and percentages will be presented for categorical and ordinal variables. Percentages will be based on the number of nonmissing values in the dose group. All study data will be presented in by-patient/patient data listings.

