10.2.3.2. Secondary Efficacy Endpoints

The secondary endpoints of the study are the change from baseline over 18 months for the following: serum TTR, mNIS+7, Norfolk QOL-DN, and PND score.

For continuous parameters, measurements will be summarized using descriptive statistics. Actual measurement, change, and percentage change from baseline to each scheduled visit will be summarized. To understand the effect of revusiran, the mean change from baseline at 18 months with the associated 80% and 95% CIs will also be summarized.

For categorical parameters, frequencies and percentages will be presented. To understand the effect of revusiran from baseline, the frequency and percentage of patients at each of the category shifts from baseline at 18 months will be summarized.

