10.2.3.3. Exploratory Endpoints

The exploratory endpoints of the study are to assess the change from baseline over 18 months for the following: mBMI, FAP stage, NIS, a grip strength test, NYHA classification, Karnofsky Performance Status, ECHO parameters, cardiac biomarkers, EQ-5D and COMPASS 31 questionnaires, and an optional exploratory residual liver tissue evaluation, if available. Analyses for these endpoints will be conducted in a similar fashion as specified for secondary efficacy endpoints.

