# **3.2.** General Methods

All data listings that contain an evaluation date will contain a relative study day (Rel Day). Pretreatment and on-treatment study days will be calculated relative to the day of the first dose of study medication which is designated as Day 0. The day preceding first dose is Day -1. The last day of study medication is designated with an "L" (e.g., Day 14L). Post-treatment study days are numbered relative to the last dose and are designated as Day 1P, Day 2P, etc.

All outputs will be incorporated into Microsoft Word or Excel files, or Adobe Acrobat PDF files, sorted and labeled according to the International Conference on Harmonisation (ICH) recommendations, and formatted to the appropriate page size(s).

For categorical variables, summary tabulations of the number and percentage of patients within each category (with a category for missing data) of the parameter will be presented. For continuous variables, descriptive statistics including the number of patients, mean, median, SD, minimum, and maximum values will be presented.

If assessments are collected in replicates (e.g., grip test, mNIS+7), then the average of the replicates will be used in the analyses.

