#### 4.3.3. Exploratory Endpoints

Analyses of secondary efficacy endpoints will be based on the Evaluable Analysis Set and Safety Analysis Set, except as noted in Section 2.1.

Descriptive statistics will be provided for actual values, change from baseline and percent change from baseline at each scheduled visit for continuous exploratory endpoints. For categorical values, the numbers and percentages of patients reporting each response will be generated.

For QOL questionnaires, summaries of each of the domains will also be generated.

Shift tables will be created for FAP stage to summarize the baseline value versus post-baseline value at each scheduled visit. An additional summary will present the shift from baseline to worst post-baseline value. Similar summaries will be provided for NYHA classification and KPS. For KPS, the categories will be defined as follows: 100-80 (able to carry out normal activity and to work; no special care needed), 70-50 (unable to work; able to live at home and care for most personal needs; varying amount of assistance needed) and 40-0 (unable to care for self; requires equivalent of institutional or hospital care; disease may be progressing rapidly).

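### The mean percent change planned for NT-proBNP, BNP and troponin T and I is biased upward, and the mean change that carries the protocol's Month 18 intervals is imprecise; a geometric mean ratio to baseline would be better.

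*Protocol*

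**What the plan says.** Protocol 8.3.8 describes sampling only: blood is "collected and analyzed for the quantification of troponin T, troponin I, N-terminal prohormone of B-type natriuretic peptide" and BNP, at a central laboratory. The analysis rules are elsewhere.

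- **Protocol 10.2.3.3** lists cardiac biomarkers among the exploratory endpoints, as change from baseline over 18 months, and adds: "Analyses for these endpoints will be conducted in a similar fashion as specified for secondary efficacy endpoints".
- **Protocol 10.2.3.2**, which is thereby carried over, says: "Actual measurement, change, and percentage change from baseline to each scheduled visit will be summarized". It also says that "the mean change from baseline at 18 months with the associated 80% and 95% CIs will also be summarized".
- **SAP 4.3.3** says: "Descriptive statistics will be provided for actual values, change from baseline and percent change from baseline at each scheduled visit for continuous exploratory endpoints". It mentions no confidence interval for exploratory endpoints.
- **SAP 3.2** defines the statistics for continuous variables: "descriptive statistics including the number of patients, mean, median, SD, minimum, and maximum values will be presented". Protocol 10.2 gives a similar list.
- **SAP 3.4** takes the last value before first dose as baseline. Averaging of pre-dose values is specified only for TTR and vitamin A.

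None of these sections mentions a log transformation, a geometric mean or a ratio to baseline for the biomarkers. None says how a value below the assay limit is to be handled.

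**The concern.** Natriuretic peptides and troponins are positive concentrations, and their changes are naturally described as multiples. On the percent scale a rise has no ceiling, while a fall cannot exceed 100%. One patient who doubles (+100%) and one who halves (-50%) average (100 - 50)/2 = +25%, although the net fold change is 2 × 0.5 = 1.00. The denominator of every percent change is a single pre-dose value, so noise in that value adds to the effect.

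The mean change in concentration units has a different weakness. The patients with the highest values supply most of it, so with about 12 patients it can reflect one or two people.

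Cardiac function is part of the exploratory objective. The study has a single arm, so no control group carries the same bias for comparison. A reader of the mean percent change row could see cardiac worsening where there is none, or miss part of a real fall.

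**Working it through.** **The plan's own figure.** The only precision figure in the documents is for TTR: 80 ± 1.96 × 6/√12 = 76.6% to 83.4%, which agrees with the stated 77% to 83%. There is no such figure for the biomarkers, so their variability has to be assumed.

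**Step 1: expected mean percent change.**
- Input from the documents: about 12 patients (protocol 3.2).
- Assumed: log(value/baseline) is normal with SD s = 0.3, 0.5 or 0.7, and true geometric mean ratio G = 1.00 (no change) or 0.80 (a 20% fall).
- Expected mean percent change = 100 × (G × exp(s²/2) - 1).
- Standard error at n = 12 = 100 × G × exp(s²/2) × √(exp(s²) - 1)/√12.
- Example, s = 0.5 and G = 1: exp(0.125) = 1.133, giving +13.3%; standard error 100 × 1.133 × 0.533/3.464 = 17.4.

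| s | Expected, no change | Standard error, no change | Expected, true 20% fall |
|---|---|---|---|
| 0.3 | +4.6% | 9.3 | -16% |
| 0.5 | +13.3% | 17.4 | -9% |
| 0.7 | +27.8% | 29.3 | +2% |

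**Step 2: how often the row points upward.** Simulated trials of 12 patients, for s = 0.3, 0.5 and 0.7:
- No true change: the mean percent change is above zero in about 68%, 77% and 83% of trials. The geometric mean ratio is above 1 in about 50%.
- True 20% fall: the mean percent change is above zero in about 2%, 23% and 49% of trials. The geometric mean ratio is above 1 in about 0.5%, 6% and 13%.

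**Step 3: a second model.** Suppose instead that each visit's value is the patient's true level times lognormal error with within-patient coefficient of variation c. With no true change, the expected mean percent change is 100 × c². That is +1% at c = 10%, +9% at 30%, +25% at 50% and +36% at 60%. The direction is the same.

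**Step 4: mean change in concentration units.** Under the Step 3 model both visits have the same distribution, so the expected mean change is exactly zero. Simulation with an assumed between-patient log-SD of 1.0 put it within 0.01% of the baseline mean for c from 10% to 60%, with a rise shown in 50% of trials. It is biased upward only under a different model, in which the log-change is independent of the observed baseline and its median ratio is 1.

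Its weakness is dominance. With an assumed baseline geometric SD of 2 to 4, s from 0.3 to 0.7 and n = 12, the patient with the largest change supplies a median of about 28% to 42% of the total absolute change. Normally distributed changes would give about 20%, so the excess due to skewness is roughly 8 to 22 percentage points.

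**Step 5: the planned median.** Under the Step 1 model with no true change, the sample median percent change averages about +0.6%, +1.7% and +3.2%, and is above zero in 50% to 51% of trials. With a true 20% fall it averages about -19.5%, -18.8% and -17.3%.

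**The case against.** The strongest reply is that the plan already contains a sound summary. The median, minimum and maximum accompany every mean, and all data are listed by patient, so with about 12 patients every value can be seen. Step 5 confirms that the median is close to the truth. The endpoint is exploratory, no test is planned for it, and the protocol's intervals are for the mean change, not the mean percent change. All of this stands, and it limits the point to the mean-based rows and the Month 18 interval. It does not remove the point, because no estimate with an interval is planned on the scale on which these markers vary.

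Three stronger readings are tempting and are not supported.

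- **That the mean change also reports a rise when nothing has changed.** If the marker's distribution is unchanged, its expectation is zero (Step 4). It is imprecise, which is a different fault.
- **That chance alone will read as cardiac worsening.** The expected bias is below one standard error at n = 12 in every scenario of Step 1. If a 95% t-interval were put on the mean percent change, its lower limit would lie above zero in only about 4% to 5% of trials with no change, against a nominal 2.5%.
- **That a real fall will be reversed.** For a 20% fall this happens in expectation only at the largest assumed SD, and then only to +2%. At the smallest SD the mean percent change is above zero in about 2% of trials.

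**Conclusion.** The concern holds for the mean percent change of the four markers. It is biased upward by an amount set by their variability: about +5% to +28% with no true change, and -16% to +2% where the true change is -20%, for log-ratio SDs of 0.3 to 0.7. The direction follows from arithmetic. The size rests on these assumed SDs and on an approximately lognormal distribution, because the documents give no biomarker variability.

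The mean change is unbiased when the distribution is unchanged, but it is a poor basis for the 80% and 95% intervals that the protocol carries over to exploratory endpoints. The consequence is modest: some rows and one interval of a descriptive exploratory table can mislead, while the median beside them does not. No primary or secondary conclusion is affected.

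**What to change.** In SAP 4.3.3, for NT-proBNP, BNP, troponin T and troponin I:

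- Analyse log(value/baseline) and report the geometric mean ratio to baseline at each scheduled visit.
- At Month 18, give 80% and 95% t-based intervals on the log scale, back-transformed. This also settles whether the protocol's intervals apply to these endpoints, on which SAP 4.3.3 is silent.
- Keep the median and range. Either omit the mean percent change for these markers or label it as not for interpretation, and record the departure from protocol 10.2.3.2 and 10.2.3.3.
- State one fixed substitution rule for values below the assay limit, and report how many values it affects for each marker and visit.

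The cost is a short SAP paragraph and a few lines of code, with no new data and no change to study conduct. Geometric means are slightly less familiar to readers. For a marker with many values below the assay limit, the result will depend on the substitution rule, which is why the count should be shown.

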8.3.9. EuroQOL Questionnaire in 5 Dimensions

Quality of life will be assessed through the use of the EuroQOL questionnaire in 5 dimensions (EQ-5D), a standardized 5-question instrument for use as a measure of health outcomes.[34]

8.3.10. Composite Autonomic Symptom Score

To evaluate changes in autonomic symptoms, patients will complete the Composite Autonomic Symptom Score (COMPASS 31) questionnaire. The questionnaire consists of 31 clinically selected questions evaluating 6 autonomic domains (orthostatic intolerance, secretomotor, gastrointestinal, bladder, and pupillomotor).[35]

8.3.11. Columbia Suicide Severity Rating Scale Questionnaire

The Columbia Suicide Severity Rating Scale (C-SSRS) will be used to assess the mental status of the patient as it relates to suicidal ideation and behavior. This questionnaire will be administered to the patient by trained study personnel.[41]

8.3.12. Pharmacoeconomics Questionnaire

Disease level and healthcare utilization will be assessed using a patient reported pharmacoeconomics questionnaire.

8.3.13. Optional Exploratory Assessment

8.3.13.1. Optional Residual Liver Tissue Evaluation

If, at any time during the study, a liver biopsy is performed per standard of care procedures, an optional evaluation of residual liver tissue may also be performed; and, if allowed by local regulations, this evaluation will include measurement of the concentration of revusiran in residual tissue and a possible evaluation of the mechanism of action for revusiran.

Details can be found in the revusiran Study Reference Manual.

9. ASSESSMENT OF SAFETY

9.1. Safety Parameters

9.1.1. Demographic and Medical History

Patient demographic data will be obtained at the Screening visit. A complete medical history will be obtained at Screening. As part of the complete medical history, if available, the prior 6 months of LFTs will also be collected. An interval medical history will be collected during the Screening/Baseline and Baseline visits and only changes in medical history will be recorded.

9.1.2. Vital Signs

Vital sign measurements include blood pressure, heart rate, oral body temperature, and respiratory rate. Vital signs will be measured in the seated or supine position (should be consistent for each patient), after the patient has rested comfortably for 10 minutes. Blood pressure should be taken using the same arm. Oral body temperature will be obtained in degrees Celsius, heart rate will be counted for a full minute and recorded in beats per minute, and respiration rate will be counted for a full minute and recorded in breaths per minute.

When vital signs are scheduled at the same time as blood samples, vital signs should be obtained before the blood sample. On dosing days, vital signs should be obtained before dosing.

For the safety of the patient, additional vital sign assessments may be added at the discretion of the Investigator.

9.1.3. Weight and Height

Height will be measured only at the Screening visit. Body weight will be measured in kilograms.

9.1.4. Physical Examination

Routine physical examinations will include the examination of the following: general appearance, head, eyes, ears, nose and throat, chest/respiratory, heart/cardiovascular, gastrointestinal/liver, musculoskeletal/extremities, dermatological/skin, thyroid/neck, lymph nodes, and neurological/psychiatric.

9.1.5. **Ophthalmologic examination**

Visual acuity should be evaluated at the beginning of each specified visit (eg, before slit-lamp examination). Manifest refraction will be performed at each specified visit, where possible, before visual acuity testing and will be used to obtain a correction for visual acuity evaluations. Visual acuity testing should be done with best (most recent) correction and be tested in bright and dim light conditions.

Further details regarding the ophthalmologic examinations will be provided in the Study Reference Manual.

9.1.6. Immunosuppressive Agent Monitoring

Blood samples for immunosuppressant monitoring will be collected at the time points in the Schedule of Assessments and for any suspected episodes of allograft rejection. Samples may also be collected at unscheduled time points when clinically indicated per local standard of care procedures. Sample analysis will take place at a local laboratory.

9.1.7. Liver Allograft Status

Patients will be monitored for possible liver allograft rejection; any biopsies performed to rule out allograft rejection will be evaluated according to the Banff Working Group on Liver Allograft Pathology criteria, a set of consensus criteria for the causes of liver allograft dysfunction.[40]

